3.1 Primary Variable

The primary variables are the:

- Number and proportion of participants experiencing ocular or non-ocular adverse events (AEs),
- Number and proportion of participants experiencing any clinically significant abnormal hematology or chemistry parameter

3.2 Secondary Variables

The secondary variables are change over time in:

- Best corrected visual acuity (BCVA),
- Schisis detected by optical coherence tomography (OCT) with infrared montage, to include volumetric analysis of schisis cavity size,
- Static and kinetic visual fields measured using the Octopus perimeter,
- Visual fields measured by microperimetry,
- Reading speed test,
- Contrast sensitivity,
- Full-field electroretinogram (ffERG),

- Multifocal electroretinogram (mfERG), and
- Quality of life questionnaire responses.

3.3 Other Outcome Variables

Other outcome variables include the following:

- Change over time in fundus photographs,
- Change over time in titers of serum antibodies or IFN-γ ELISPOT responses to retinoschisin (RS1).
- Change over time in serum antibodies and IFN-γ ELISPOT responses to AAV, and
- The number and proportion of participants with rAAV2tYF-CB-hRS1 vector DNA detectable in blood by polymerase chain reaction (PCR) assay.

4. Study Design and Procedures

4.1 General Study Design

This is a non-randomized, open-label, Phase 1/2 dose escalation study of the safety and efficacy of rAAV2tYF-CB-hRS1 administered by intravitreal injection in one eye in individuals with XLRS. The primary objective is to evaluate safety and the secondary objective is to evaluate efficacy.

Each participant is to receive rAAV2tYF-CB-hRS1 by intravitreal injection in one eye on a single occasion as outlined in the schematic below.

		Number of Dose Level				
Group ^a	Age (yr)	Subjects	vg/mL	Volume	vg per eye	
1A	≥ 18	3	1.43 × 10 ¹²	0.07 mL	1 × 10 ¹¹	
1B	≥ 18	3	1.43 × 10 ¹²	0.07 mL	1 × 10 ¹¹	
2	≥ 18	3	4.3 × 10 ¹²	0.07 mL	3 × 10 ¹¹	
2A	6-17	Up to 6	4.3 × 10 ¹²	0.07 mL	3 × 10 ¹¹	
3	≥ 18	3	4.3 × 10 ¹²	0.14 mL	6 × 10 ¹¹	
4	≥ 6	Up to 15	MTD ^b	MTD	MTD	

Schematic of Study Design:

^a Visual acuity not better than 58 Early Treatment Diabetic Retinopathy Study (ETDRS) letter score in Group 1A, 63 in Groups 1B, 2, 2A & 3, 68 in Group 4.

^b MTD = maximum tolerated dose determined in Groups 1A, 1B, 2 and 3 for adults, in Groups 1A, 1B, 2, and 3 (adult participants only) and 2A (pediatric participants only) for pediatric participants.

Participants in Groups 1A, 1B, 2 and 3 are at least 18 years of age and receive the vector at a lower dose (Groups 1A and 1B), middle dose (Group 2) or higher dose (Group 3). Participants in Group 1A have visual acuity that is worse than participants in subsequent groups (ETDRS letter score of 58 in Group 1A and 68 in other groups). Participants in Group 2A will be 6-17 years of age and receive the

vector at the middle dose level. Participants in Group 4 will be at least 6 years of age and will receive the vector at the maximum tolerated dose (MTD) determined in Groups 1A, 1B, 2, and 3 for adults; in Groups 1A, 1B, 2, and 3 (adult participants only) and 2A (pediatric participants only) for pediatric participants.

Participants in all groups are selected from individuals who are not being treated with a carbonic anhydrase inhibitor during the study and have not been treated with any carbonic anhydrase inhibitor within the 3 months prior to enrollment in the study. Participants are asked not to begin treatment with a carbonic anhydrase inhibitor within 6 months after study agent administration.

Individuals who have participated in the natural history study XLRS-001, entitled "Clinical Evaluation of Individuals with XLRS", may have discontinued their participation in that study and enrolled in this study if all appropriate entry criteria were met. In this case, results of the evaluations from the most recent visit in the natural history study could be used as part of the appropriate screening visit evaluations for this study, as long as all the evaluations were conducted according to the Study Manual of Procedures and Reading Center Manual of Procedures of this study, and the visit occurred no more than 3 months prior to the planned date of study agent administration. If the most recent visit examinations are performed.

Enrollment began with Group 1A and will proceed to subsequent groups after review of safety data by a Data and Safety Monitoring Committee (DSMC). After review of safety data from Group 1A, participants will be enrolled in Groups 1B and 2 concurrently. After review of safety data from Groups 1A, 1B and 2, participants will be enrolled in Group 3. After review of safety data from Groups 1A, 1B, 2, and 3, participants \geq 18 years of age will be enrolled in Group 4. As ocular inflammation has been seen in the first 12 subjects enrolled in the study and pediatric participants might be more prone to inflammation, pediatric participants (age 6-17) in this study will first be treated at the middle dose (Group 2A) prior to the enrollment in Group 4.

Within groups 1A, 2, 2A and 3, enrollment of participants will be staggered by at least 2 weeks to allow adequate time for review of safety information by the investigators and sponsor.

Within group 4, enrollment of the first 3 pediatric participants will be staggered by at least 2 weeks to allow adequate time for review of safety information by the investigators and sponsor.

Approximately 27 participants are to be enrolled in this study. Enrollment in this study is anticipated to take approximately 30 months. Enrolled participants will have frequent follow-up visits during the first year after study agent administration.

To monitor for delayed AEs and assess the duration of any changes in visual function or structure that occur, participants are followed annually for an additional 4 years after the Month 12 visit.

4.2 Schedule of Visits and Assessments

The schedule of visits and assessments is provided below.

Time relative to study				D	ay				Мо	onth			Year	
agent administration	Screen ^a	BL⁵	0	1	7	14	1	2	3	6	9	12	2-5°	ETd
Visit Number	1	2	3	4	5	6	7	8	9	10	11	12	13-16	
Informed consent/assent	√													
Inclusion/exclusion criteria	✓	✓												
Initial medical history	√													
Blood for DNA testing ^e	√													
Physical exam ^f	✓													
Safety labs ^{f,g}	√				✓	✓								√*
Coagulation (PT and PTT) ^f	✓													
Blood for AAV antibodies	✓						✓		✓	✓		✓	✓	✓
Blood for RS1 antibodies		✓					✓		✓			✓	✓	~
Blood for PBMC		✓					✓	✓	✓					√*
Blood for vector DNA		✓		✓	✓	✓								√*
Prophylaxis for inflammation		✓												
Study Agent Administration			✓											
Clinical Evaluation ^h		✓	✓	✓	✓	✓	✓	✓	✓	✓	✓	✓	✓	~
Adverse Event Review		✓	✓	✓	✓	✓	✓	✓	✓	✓	✓	✓	✓	~
Ophthalmic Examinations ⁱ	√	✓	✓	✓	✓	✓	✓	✓	✓	✓	✓	✓	✓	~
Visual Acuity	√	×2		✓	✓	✓	✓	✓	✓	✓	✓	✓	✓	~
Octopus visual fields	√	×2					✓	✓	✓	✓	✓	✓	✓	~
Microperimetry	~	×2					✓	✓	✓	✓	✓	~	~	~
Reading speed	√	×2							✓	✓	✓	✓	✓	~
Contrast Sensitivity	√	×2							✓	✓	✓	✓	✓	~
Electroretinography ^j	✓	✓							✓	✓		✓	√j	~
Optical Coherence Tomography	~	×2					~	~	~	~	~	~	~	~
Fundus Photography		✓										✓		~
Quality of life questionnaire	✓	✓							✓	✓	✓	✓	✓	✓

^a The screening visit should occur within 3 months before study agent administration.

^b The baseline (BL) visit should occur within 7 days before study agent administration.

^c Long-term follow-up (LTFU) evaluations once a year for years 2-5.

^d An early termination (ET) visit will be sought for any subject who withdraws from the study before the Year 1 visit. Perform the evaluations indicated as ✓* if the ET visit occurs before the last visit at which these tests are required.

^e DNA testing for participants who have not had a mutation in the *RS1* gene documented previously.

^f Physical exam, safety labs and coagulation may be obtained at either the screening or baseline exam.

^g Safety labs include hematology and clinical chemistry as specified in Section Error! Reference source not found..

^h Clinical evaluation consists of an interim medical history, including use of carbonic anhydrase inhibitors and other medications, review of AEs, and a symptom-directed physical examination.

¹ Ophthalmic examinations include slit lamp examination, tonometry, indirect ophthalmoscopy and retinal biomicroscopy in both eyes will be evaluated at each visit, except on Day 0 (Visit 3) when the only required exam is tonometry of the study eye about 30 minutes after study agent administration is completed.

¹ ERG testing at LTFU visit if a significant change seen in ERG at month 12 visit compared to screening and baseline visits.

5. Study Treatment

All subjects will receive rAAV2tYF-CB-hRS1, a replication-incompetent, recombinant adeno-associated virus (rAAV) vector that expresses the RS1 protein after the vector enters retinal cells. The dose level of each group is described in the schematic of study design shown in section 4.1.

The per protocol (PP) population is a subset of the safety population and includes the subjects who complete the study with no major protocol deviations. Major protocol deviations include inclusion/exclusion criteria deviations and use of prohibited medications. Additional analysis may be conducted on the PP population.

9. General Statistical Considerations

9.1 Unit of Analysis

The unit of analysis in this study will be the study eye for all applicable efficacy and safety summaries. In this study, only the study eye will receive treatment with the study drug. The study eye is defined as the eye with the worse visual acuity at the baseline visit. If both eyes have the same visual acuity, the choice of study eye will be determined at the discretion of the investigator in consultation with the participant. Additionally, non-ocular AEs and medical history will be presented at the subject level.

9.2 Missing or Inconclusive Data Handling

Missing data will be treated as missing and no imputation will be performed unless otherwise specified.

9.3 Definition of Baseline and Pretreatment

Values from the baseline visit (or an average for multiple baseline values) will be considered baseline values for any variables that are analyzed over time. If baseline visit data were not collected, then screening values will be used as baseline values. Pretreatment values will be all values collected at screening or baseline visits.

9.4 Data Analysis Conventions

All data analysis outlined in this SAP will be performed by Statistics & Data Corporation (SDC). Statistical programming and analyses will be performed using SAS[®] Version 9.4 or higher. Output will be provided in Rich Text Format (RTF) for tables and figures and Portable Document Format (PDF) for tables and listings using landscape orientation. All study data for treated subjects will be listed by group, subject, and visit (as applicable) unless otherwise specified. Only a disposition listing will be created for screen failed subjects.

Summaries for continuous and ordinal variables will include the number of observations (n), arithmetic mean, standard deviation (SD), median, minimum, and maximum. Minima and maxima will be reported with the same precision as the raw values; means and medians will be presented to one additional decimal place than reported in the raw values. Standard deviations will be presented to two additional decimal places than reported in the raw values. Summaries for discrete variables will include frequency counts and percentages. All percentages will be rounded to one decimal place (i.e., XX.X%). Change from baseline will be calculated as follow-up visit values minus the baseline value.

All statistical tests will be two-sided with alpha level of 0.05. Unless otherwise specified, summaries will be presented by group (1A, 1B, 2, 2A, 2+2A, 3, 4, 3+4, and all subjects) and, where appropriate, visit.

Unscheduled visits will not be summarized. Study visits will be referred to in all tables and listings with the expected study day/month/year corresponding to the visit to enable reviewers to understand the assessment timing without referring to the protocol visit schedule. The following table shows the scheduled study visits, their planned study day:

Scheduled Visit	Planned Study Day
Visit 1	Screening
Visit 2	Baseline
Visit 3	Day 0
Visit 4	Day 1
Visit 5	Day 7
Visit 6	Day 14
Visit 7	Month 1
Visit 8	Month 2
Visit 9	Month 3
Visit 10	Month 6
Visit 11	Month 9
Visit 12	Month 12
Visit 13	Year 2
Visit 14	Year 3
Visit 15	Year 4
Visit 16	Year 5
1	

10. Disposition of Subjects

The following disposition items will be summarized:

- The number of subjects screened (who signed the informed consent/assent form)
- The number of screen failures
- The number of subjects enrolled (who met the enrollment criteria)
- The number of subjects treated (who received an intravitreal injection of study agent)
- The number and percentage of subjects who completed the study
- The number and percentage of subjects who withdrew from the study and the reasons for premature discontinuation
- The number and percentage of subjects with any major deviations

All percentages will use the number of subjects treated as the denominator, unless indicated otherwise.

In addition, disposition and protocol deviation listings will be provided.

11. Demographic and Pretreatment Variables

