### **1.3.2** Adequacy of Protection from Potential Risks

The medical history and physical examination performed during the screening and baseline visits will identify individuals with ophthalmologic or other medical conditions that would increase the risks associated with participation in the study. Results of all laboratory and safety evaluations will be reviewed by the investigator and sponsor throughout the trial, and the DSMC will review safety data from completed dosage level groups before enrollment into subsequent dosage level groups (see Section 7.4).

Intravitreal injection of the study agent will be performed by experienced personnel with strong attention paid to aseptic technique to avoid the risks listed above. Participants will be followed up at frequent study visits with clinical evaluation and ophthalmic examination to prevent and/or mitigate the risks associated with steroid use.

Participants will be provided with telephone numbers to contact the investigators for any questions or concerns about possible post-procedure complications or side effects from study agent administration, and will be promptly evaluated and treated if necessary to minimize the consequences of any complications.

To minimize the likelihood of pain and bruising, phlebotomy will be performed by experienced phlebotomists.

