The participant will be instructed to notify the investigator immediately if symptoms of eye pain, redness, photophobia or diminished vision develop.

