### 6.9 **Ophthalmic Examinations**

Ophthalmic examinations of both eyes will be performed at the screening and baseline visits and at each visit after study agent administration, including each long-term follow-up visit. These examinations will include slit lamp examination, tonometry, indirect ophthalmoscopy and retinal biomicroscopy. Signs of inflammatory responses will be quantified using a standard 0 to 4+ cells and flare grading system [59]. On the visit at which the study agent is administered, IOP in the study eye will be measured about 30 minutes after study agent administration is completed.

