14.5 Slit-Lamp Biomicroscopy Examination

A dilated slit-lamp examination will be performed using the investigator's standard procedure. Documentation will include the presence or absence of central and peripheral schisis.

08 August 2017

A slit-lamp biomicroscopy examination of the cornea, conjunctiva, anterior chamber, iris, lens, and vitreous will be performed at each visit.

Shifts from baseline to worst value during follow-up will be tabulated. A subject listing of the slit-lamp biomicroscopy parameters will also be produced.

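### SAP 9.4 leaves unscheduled visits out of summaries with no exception, so the slit-lamp and ophthalmoscopy shift-to-worst tables may understate the worst finding

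*SAP*

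**What the plan says.** SAP 9.4 (Data Analysis Conventions) states "Unscheduled visits will not be summarized". The sentence carries no exception. It is followed by a table of scheduled visits, Visit 1 (Screening) to Visit 16 (Year 5), which does not list the early termination visit.

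SAP 14.5 (slit lamp) states "Shifts from baseline to worst value during follow-up will be tabulated", and SAP 14.7 (indirect ophthalmoscopy) uses the same sentence. Neither section says whether unscheduled examinations count. The resulting outputs are Tables 14.4.5 and 14.4.7.

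The slit-lamp table covers the structures where intraocular inflammation is seen: "A slit-lamp biomicroscopy examination of the cornea, conjunctiva, anterior chamber, iris, lens, and vitreous will be performed at each visit". Protocol 6.9 adds the scale: "Signs of inflammatory responses will be quantified using a standard 0 to 4+ cells and flare grading system".

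The protocol makes examinations between visits foreseeable. Under Protocol 5.4, participants are told to "notify the investigator immediately if symptoms of eye pain, redness, photophobia or diminished vision develop". Protocol 1.3.2 says that participants with possible complications "will be promptly evaluated and treated if necessary to minimize the consequences of any complications".

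The listings are complete. SAP 9.4 also provides that "All study data for treated subjects will be listed by group, subject, and visit (as applicable) unless otherwise specified".

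**The concern.** A programmer who follows SAP 9.4 would take the maximum over the scheduled visits in its table and present it as the worst value over follow-up. If a participant's worst grade was recorded only at an examination prompted by symptoms, the shift table would show a lower grade than the one observed. SAP 9.2 rules out imputation unless otherwise specified, so nothing would recover the omitted value.

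This matters because safety is the primary objective. SAP 4.1 reports that ocular inflammation had already been seen in the first 12 subjects. Protocol 7.2 names slit lamp, tonometry and indirect ophthalmoscopy as the principal means of detecting ocular adverse events. A shift-to-worst table is meant to show how far the eye departed from baseline at any time, so a rule that can hide the furthest departure defeats its purpose.

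**Working it through.** **Plan figures.** The plan states no number for these tables. Its only precision figures are the upper limits for dose-limiting toxicity with no events. They reproduce as 1 − 0.025^(1/n): 33.63% for n = 9 and 12.77% for n = 27. They play no part here.

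**Step 1: direction.** Let S be the set of scheduled post-treatment examinations and A the set of all post-treatment examinations. S is contained in A, so max over S ≤ max over A. Leaving examinations out can lower a participant's worst value or leave it unchanged, but never raise it.

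**Step 2: weight of one participant.** Group sizes come from the design table (3, up to 6, up to 15) and the approximate total of 27. One misclassified participant moves a percentage by 100/n:

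- n = 3: 33.3 points
- n = 6: 16.7 points
- n = 15: 6.7 points
- n = 27: 3.7 points

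**Step 3: how often scheduled visits could miss the worst grade.** The documents give no episode length, inflammation rate or number of unscheduled visits, so this is an illustration on stated assumptions.

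- Scheduled examinations on Days 1, 7 and 14, at Months 1, 2, 3, 6, 9 and 12, then yearly (SAP 9.4). In days: 1, 7, 14, 30.4, 60.9, 91.3, 182.6, 273.9, 365.25, then every 365.25.
- Visits fall exactly on the nominal day.
- Each participant has one interval of D days at the worst grade, with onset uniform over the window shown. D = 7, 14, 28 and 42 are assumed.

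Within a gap of g days, the chance of falling on no scheduled visit is max(0, 1 − D/g). Over a window of several gaps, it is the sum of max(0, g − D) divided by the window length.

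For onset from Day 0 to Month 3, the gaps are 1, 6, 7, 16.4, 30.5 and 30.4 days (total 91.3):

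- D = 7: (9.4 + 23.5 + 23.4)/91.3 = 56.3/91.3 = 62%
- D = 14: (2.4 + 16.5 + 16.4)/91.3 = 35.3/91.3 = 39%
- D = 28: (2.5 + 2.4)/91.3 = 4.9/91.3 = 5%
- D = 42: 0%

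For onset from Month 3 to Month 12, each gap is about 91.3 days. D = 14 gives 1 − 14/91.3 = 85%, and D = 42 gives 1 − 42/91.3 = 54%. All windows:

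| Onset window | D = 7 | D = 14 | D = 28 | D = 42 |
|---|---|---|---|---|
| Day 0 to Month 1 | 31% | 8% | 0% | 0% |
| Day 0 to Month 3 | 62% | 39% | 5% | 0% |
| Month 3 to Month 12 | 92% | 85% | 69% | 54% |
| After Month 12 | 98% | 96% | 92% | 89% |

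**Step 4: what these percentages mean.** They are chances that scheduled visits alone miss the interval. The table is understated through SAP 9.4 only if, in addition, the participant was examined off schedule during that interval and the finding was recorded.

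**The case against.** The strongest reply is that the SAP 9.4 sentence introduces a paragraph on visit labels, so it may be only a rule for by-visit displays. On that reading, the more specific text in 14.5 and 14.7 already takes in every examination. The reading is possible, but the SAP does not adopt it, and the literal reading is the one a programmer would be safest in following. The point therefore stands as a conflict to be resolved, with no certainty about which reading would be programmed.

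The timing of risk also favours the plan. Protocol 1.2.2 reports that inflammation in nonhuman primates peaked about 4 weeks after dosing and then improved over the next 2 months. Visits at Days 1, 7 and 14 and Months 1, 2 and 3 cover that period well. This stands, and it is why the high miss rates after Month 3 should not be quoted alone.

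Four stronger readings are tempting but unsupported:

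- **The primary safety result is biased.** Protocol 7.1.1 makes Grade 3 or 4 adverse events over 12 months the primary parameter, and SAP 3.1 names adverse events and laboratory abnormalities. SAP 14.1 recognises events found when a participant presents for care, and its tables count participants whatever the visit type. An off-schedule event recorded as an adverse event is still tabulated.
- **Unscheduled visits are where inflammation is most likely to be seen.** This is an inference from symptom-triggered contact. No passage says so, or says what is examined and graded at such visits.
- **These are the only tables of graded cells and flare, or are titled as worst value.** SAP 14.5 lists anatomical structures, and both tables are titled simply as shift tables.
- **The IOP table has the same fault.** SAP 14.6 promises by-visit summaries and no worst value, so nothing there conflicts with 9.4. A maximum over all post-dose readings would also mix in the Day 0 reading taken about 30 minutes after injection.

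The adverse event tables do not make the point moot. SAP 14.1 grades intensity by interference with daily activities and need for intervention, which is a different scale from the examination grade.

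**Conclusion.** The concern holds in a limited form. SAP 9.4 is not reconciled with the worst-value text in 14.5 and 14.7. Read literally, it restricts Tables 14.4.5 and 14.4.7 to scheduled visits. Those tables then may understate the worst finding, and any error favours safety. It arises only where a participant's worst grade was seen solely off schedule.

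The size cannot be computed from the documents. On the assumptions of Step 3, misses are rare for long early episodes and common for short episodes or those starting after Month 3. With groups as small as 3, a single case would be visible. It is a defect in two supporting safety tables that should be corrected, and it does not call the primary safety analysis into question.

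**What to change.** Replace the sentence in SAP 9.4 with:

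> Unscheduled visits will not be included in by-visit summaries, but all post-treatment examinations, including unscheduled and early termination visits, will be included in the worst-value shift tables (14.4.5, 14.4.7).

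Naming early termination closes a second gap: the schedule of assessments requires ophthalmic examinations at that visit, but the SAP 9.4 visit table omits it.

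The cost is one sentence and minor programming. No new assessments are needed, provided that off-schedule examination findings are entered in the eCRF, which the documents do not spell out and the sponsor should confirm. The safety tables may look slightly less favourable.
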